NON-INTERVENTIONAL (NI) STUDY PROTOCOL

| | |
|---|--|
| Title | Provider Referral Patterns Following Nephrectomy in High-Risk Locoregional Renal Cell Carcinoma |
| Protocol number | A6181230 |
| Protocol version identifier | Final Version 4 (Amendment 1) |
| Date | 27 March 2020 |
| Research question and objectives | To estimate the proportion of patients diagnosed with locoregional renal cell carcinoma who are at high risk for recurrence following nephrectomy, describe referral patterns, and characterize treatment in this population. Outcomes including estimation of the incidence of recurrence and disease-free interval following nephrectomy will be reported overall and among the subgroup of patients receiving adjuvant systemic therapy with sunitinib following nephrectomy. |
| Authors | 
Pfizer Inc.:
 
[REDACTED] PharmD, MSc
 
[REDACTED]
 
Duke University's School of Medicine and Health System:
 
[REDACTED] MD
 
[REDACTED]
 
RTI Health Solutions:
 
[REDACTED] MS
 
[REDACTED]
 
[REDACTED] PhD
 
[REDACTED]
 |

This document contains confidential information belonging to Pfizer. Except as otherwise agreed to in writing, by accepting or reviewing this document, you agree to hold this information in confidence and not copy or disclose it to others (except where required by applicable law) or use it for unauthorized purposes. In the event of any actual or suspected breach of this obligation, Pfizer must be promptly notified.

2. LIST OF ABBREVIATIONS

| Abbreviation | Definition |
|--------------|---|
| AE | adverse event |
| AEM | adverse event monitoring |
| AIC | Akaike information criteria |
| CI | confidence interval |
| DCF | data collection form |
| ECOG | Eastern Cooperative Oncology Group |
| EMR | electronic medical record |
| HCRU | health care resource utilization |
| IEC | independent ethics committee |
| IRB | institutional review board |
| KPS | Karnofsky Performance Scale |
| NIS | non-interventional study |
| OQA | RTI-HS Office of Quality Assurance |
| RCC | renal cell carcinoma |
| RTI | RTI International |
| RTI-HS | RTI Health Solutions |
| SSIGN | stage, size, grade, and necrosis (score) |
| TNM | tumor, node, metastasis (cancer staging system) |
| UISS | UCLA Integrated Staging System |
| US | United States |

4. ABSTRACT

Provider Referral Patterns Following Nephrectomy in High-Risk Locoregional Renal Cell Carcinoma

Version 4 (27 March 2020)

Background and rationale: In 2017, renal cell carcinoma (RCC) accounted for nearly 4% of new cancer cases in the United States. Among patients initially diagnosed with regional or distant disease, 5-year survival is 67% and 12%, respectively. Although only 16% of patients are initially diagnosed with regional disease, up to 40% will experience relapse with distant metastases following nephrectomy. The high rate of recurrence among these patients highlights a continued unmet need for effective adjuvant treatment that can reduce recurrence risk, prolong the disease-free interval, and/or improved overall survival.

Yet, it is unclear whether postnephrectomy patients in real-world practice settings are typically assessed for recurrence risk postoperatively and whether patients at high risk of recurrence are seen by providers who can evaluate candidacy for adjuvant therapy, clinical trials, or alternative surveillance schedules. Additional evidence is needed to understand referral patterns and follow-up care following nephrectomy for patients at high risk of recurrence. Results from this study may provide needed evidence to understand populations of patients who are at the greatest risk of disease recurrence and investigate possible areas of unmet surveillance and treatment needs.

Objectives: To estimate the proportion of patients diagnosed with locoregional RCC who are at high risk for recurrence following nephrectomy, describe referral patterns, and characterize treatment in this population. Exploratory analyses may include estimation of the incidence of recurrence and disease-free interval following nephrectomy, if data are available.

Study design: Non-interventional, retrospective medical record review of patients diagnosed with locoregional RCC who received a nephrectomy in Duke University's health system (Duke). Using a published algorithm (eg, the UCLA Integrated Staging System [UICC] or the stage, size, grade, and necrosis [SSIGN] score) or adaptation of a published algorithm, patients at high risk of recurrence following surgery will be followed until the end of their patient record, death, or disease recurrence to examine referral patterns, receipt of systemic therapy, disease recurrence, and death. The study will consist of a pilot phase to test the data abstraction tool and determine feasibility of assessing the study objectives with available data and a full abstraction phase to compile the necessary data, conduct the analyses, and generate the documents for dissemination of the study results.

Population: Patients aged 18 years or older who were diagnosed with locoregional RCC and underwent nephrectomy at Duke between 01 April 2014 and 31 December 2019. The final date range for patient inclusion was determined after the part 2 data collection was complete.

Variables: Background (eg, age at nephrectomy, sex) and baseline clinical characteristics (eg, performance status, TNM [tumor, node, metastasis] stage, histology, tumor grade, categorical risk of recurrence following nephrectomy by commonly used clinical nomograms); postnephrectomy treatment and referrals; and disease recurrence events and survival will be assessed, where available.

Data sources: Duke researchers will abstract the necessary information from the electronic medical records of eligible patients and enter deidentified information into the study database. This study is retrospective; therefore, the collection of data will in no way influence prescribing patterns or treatment decisions.

Study size: Data will be abstracted from a target of 20 eligible patients during the pilot phase. During full abstraction, data for approximately 650 patients will be targeted for abstraction.

Data analysis: Descriptive summary of baseline characteristics by UISS risk categories among patients with locoregional RCC. Among patients at high risk of recurrence, descriptive summary of postnephrectomy follow-up care. Time-to-event outcomes (eg, disease-free interval) will be described using the Kaplan-Meier method, if feasible.

Milestones: Key milestones include finalization of the protocol (December 2018), finalization of the data-collection form (January 2019), completion of ethics submission (January 2019), completion of pilot phase and finalization of feasibility memo (June 2019), start of data collection (July 2019), completion of part 2 data collection (September 2019), completion of part 2 data analysis (November 2019), and finalization of the part 2 study report (December 2019). Additional key milestones relevant to the expanded data collection include finalization of the updated protocol (Q1 2020), completion of ethics submission (Q1 2020), start of expanded data collection (Q2 2020), completion of expanded data collection (Q2 2020), completion of expanded data analysis (Q2 2020), and finalization of the updated study report (Q3 2020).

5. AMENDMENTS AND UPDATES

| Amendment Number | Date | Protocol Section(s) Changed | Summary of Amendment(s) | Reason |
|------------------|---------------|---|---|---|
| 1 | 11 June 2019 | 9.1. Study design 9.2.1. Inclusion criteria | The study period is now 01 April 2014 to 31 March 2019. | The study period has been updated to reflect the most recent 5-year period available in the data. The pilot phase feasibility study demonstrated that a 5-year period is more than sufficient to achieve the minimum desired sample size of 500 eligible patients. |
| 2 | 27 March 2020 | Section 4 and Section 9 Section 4 and Section 9 Section 4 and Section 6 | Update date ranges throughout to reflect a study period through 31 December 2019. Increase the number of patient records abstracted to 650. Update study timeline and milestones. | The new Common Rule does not require dates for retrospective studies. Updating the date limitation will allow for nephrectomies from 2019 to be collected and for follow-up to extend through the most recent medical record entry for previously identified patients. Increase the number of subjects to include patients who have had more recent nephrectomies (up to 650 total). |

6. ANTICIPATED MILESTONES

| Milestone | Planned Date |
|--------------------------------------|--------------|
| Final protocol | 18 Dec 2018 |
| Submit IRB applications | 18 Jan 2019 |
| Feasibility assessment (pilot phase) | 05 Jun 2019 |
| Start of full data collection | 01 Jul 2019 |
| End of full data collection | 15 Sep 2019 |
| Final analytic results | 11 Dec 2019 |
| Final study report | 31 Dec 2019 |
| Final updated protocol | Q1 2020 |
| Submit revised IRB application | Q1 2020 |
| Start expanded data collection | Q2 2020 |
| End expanded data collection | Q2 2020 |
| Final updated analytic results | Q2 2020 |
| Final updated study report | Q3 2020 |

IRB = institutional review board.

7. RATIONALE AND BACKGROUND

In the United States (US), renal cell carcinoma (RCC) accounts for nearly 4% of new cancer cases and resulted in an estimated 14,400 deaths in 2017 (National Cancer Institute, 2018).¹¹ Five-year survival for patients with RCC is 74%; however, prognosis varies by disease stage. Among patients initially diagnosed with regional or distant disease, 5-year survival is 67% and 12%, respectively.

Nephrectomy is the recommended treatment for most patients with localized or regional disease, followed by surveillance (Motzer et al., 2017).¹⁰ Although only 16% of patients are initially diagnosed with regional disease, up to 40% will experience relapse with distant metastases following nephrectomy (Janzen et al., 2003; Breda et al., 2007).^{6,2} The high rate of recurrence among these patients highlights a continued unmet need for effective adjuvant treatment that can reduce recurrence risk, prolong the disease-free interval, and/or improve overall survival.

Yet, it is unclear whether postnephrectomy patients in real-world practice settings are typically assessed for recurrence risk postoperatively and whether patients at high risk of recurrence are seen by providers who can evaluate candidacy for adjuvant therapy, clinical trials, or alternative surveillance schedules. Additional evidence is needed to understand postoperative referral patterns and follow-up care for patients at high risk of recurrence.

In this study, researchers at Duke University's School of Medicine and Health System (Duke) and RTI Health Solutions (RTI-HS) will collaborate on a non-interventional, retrospective medical record review study aimed at examining postnephrectomy referral patterns and treatment characteristics in patients diagnosed with RCC. The feasibility of estimating disease recurrence and disease-free interval following nephrectomy in this population will also be explored. Results from this study may provide needed evidence to understand the proportion of postnephrectomy patients who are at the greatest risk of disease recurrence and investigate possible areas of unmet surveillance and treatment needs.

8. RESEARCH QUESTION AND OBJECTIVES

The aim of this study is to estimate the proportion of patients diagnosed with RCC who are at high risk for recurrence following nephrectomy, describe referral patterns, and characterize treatment in this population. Exploratory analyses may include estimation of the incidence of recurrence and disease-free interval following nephrectomy, if data are available. Data for this study will be collected from a retrospective medical record review of patients diagnosed with locoregional RCC who underwent nephrectomy at Duke. The following primary objectives will be assessed:

- Describe patient demographic and clinical characteristics of patients diagnosed with locoregional RCC who underwent nephrectomy.
- Estimate the proportion of patients at high risk of recurrence following nephrectomy.

- Characterize postoperative provider referrals among patients at high risk of recurrence, including the proportion of patients who were referred to other providers and reasons for referral.
- Describe treatment characteristics following nephrectomy among patients at high risk of recurrence, including the proportion of patients who received systemic therapy, type of systemic therapy received, dose and duration of treatment, reasons for treatment discontinuation, and participation in clinical trials, where available; perform subgroup analyses to describe treatment details among the subgroup of patients receiving adjuvant systemic therapy with sunitinib.
- Estimate the incidence of disease recurrence and duration of the disease-free interval following nephrectomy among all patients at high risk of recurrence, and among the subgroup of patients receiving adjuvant systemic therapy with sunitinib.

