9.1. Study Design

This study is a retrospective, observational medical record review of patients diagnosed with locoregional RCC who received a nephrectomy at Duke between 01 April 2014 and 31 December 2019. The date of the nephrectomy will be considered the *index date*.

Background clinical characteristics such as date of initial and locoregional RCC diagnoses will be identified during the period prior to the index date. Recurrence risk status will be assigned at the index date, using information available in the record at or around the index date. During the follow-up period (ie, the period between the index date and the last entry in the medical record, death, or disease recurrence), outcomes including treatment, referrals, and disease recurrence will be assessed for patients who were determined to have been at high risk of recurrence following their nephrectomy, where data are available. Figure 1 provides a visual schematic of relevant observation periods.

Figure 1. Patient Observation Periods

RCC = renal cell carcinoma.

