9.1.3. Part 3: Expanded Data Collection

Results from the part 2 study indicated that referral and treatment patterns show an increasing trend from 2018 into 2019. To further capture this trend, an additional sample of all patients with nephrectomies occurring through 31 December 2019 will be abstracted. The additional sample size during this period is estimated to be approximately 115-150 patients, for a full

combined sample of up to 650 patients in total. In addition, expanded follow-up data (ie, referral patterns, treatment patterns, and outcomes) will be collected for previously identified patients at high risk of recurrence, to include follow-up dates through the most recent available medical record entry prior to the abstraction date.

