9.2. Setting

Data will be abstracted from the Duke EMR system. Patients whose data will be included in the study will have met the criteria described in [Sections 9.2.1](#) and 9.2.2. Refer to [Figure 1](#) for a depiction of the follow-up period. No minimum follow-up time will be required. Outcomes among patients who are determined to be at high risk of recurrence will be observed over each patient's follow-up period—from the date of nephrectomy to death, disease recurrence, or the last date in their medical record (whichever occurs first).

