9.7. Data Analysis

All variables described in [Section 9.3](#) will be summarized descriptively through the tabular display of mean values, 95% confidence intervals (CIs), medians, quartiles, and standard deviations of continuous variables of interest and frequency distributions for categorical variables. All open-ended text fields associated with the “other” answer option will be evaluated and described, as appropriate.

All study-eligible patients will be included in descriptive analyses of variables pertaining to patient characteristics, baseline clinical characteristics, and initial postoperative follow-up visits (see [Sections 9.3.1](#), [9.3.2](#), and [9.3.3](#) for details). Patients who are categorized as having a high risk of recurrence will be included in additional analyses described below. Risk classification will be assessed using published algorithms (eg, UISS and SSIGN score) or adaptation of a published algorithm. The primary risk classification system used to designate the high-risk subgroup for this study will be chosen based on completeness of data available in the patient medical records. Completeness will be assessed during the pilot study. If data are available to support more than one classification system, the UISS risk classification will be used. If some data are not available to support classification using a published algorithm, an adapted version of an algorithm will be explored.

Additional descriptive analyses performed within the high-risk subgroup will include referral patterns, treatment patterns, and health outcomes (see [Sections 9.3.4](#), [9.3.5](#), [9.3.6](#)). In addition to descriptive analyses, time-to-event measures (ie, time to recurrence, overall survival) will be assessed. To adjust time-to-event measures, a Kaplan-Meier method that accounts for right-censoring will be implemented (Klein and Moeschberger, 2005).⁷ To evaluate time to recurrence, the endpoint will be programmed with the date of recurrence or date of death, whichever occurs first, as an eligible event; if neither of these events occurred, the outcome will be right censored at the date of the last medical record follow-up. To evaluate overall survival, the endpoint will be programmed with the date of death as an eligible event or right censored at the date of the last medical record follow-up.

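### The sunitinib subgroup's disease-free interval, timed from nephrectomy, includes time that is event-free by selection, and the plan neither corrects nor labels this

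*Combined protocol and SAP*

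**What the plan says.** The title-page objectives, which also cover how often recurrence occurs, state that the "disease-free interval following nephrectomy will be reported overall and among the subgroup of patients receiving adjuvant systemic therapy with sunitinib following nephrectomy". Section 8 lists the same pair of estimates among the primary objectives, "among all patients at high risk of recurrence, and among the subgroup of patients receiving adjuvant systemic therapy with sunitinib", although its opening paragraph calls them exploratory and subject to data availability.

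Nephrectomy is the index date (Section 9.1), and endpoint dates leave the site only as days from nephrectomy (Section 10). The parent group is defined at that date: "Recurrence risk status will be assigned at the index date, using information available in the record at or around the index date". Treatment is not. Section 9.1 ascertains it during follow-up, which runs from the index date to the "last entry in the medical record, death, or disease recurrence), outcomes including treatment, referrals, and disease recurrence will be assessed". Section 9.2 likewise ends observation at the first of death, recurrence or last record.

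In Section 9.7 the event is recurrence or death, whichever comes first, and "a Kaplan-Meier method that accounts for right-censoring will be implemented". That section does not mention the sunitinib subgroup. It also plans exploratory Cox models whose candidate covariates include type and duration of systemic treatment, with a hazard ratio reported for each covariate retained. No time-dependent coding is stated. The limitations in Section 9.9 cover generalisability, care outside the health system and data-entry error.

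**The concern.** The subgroup is defined by something that happens after the clock starts. Adjuvant sunitinib can be recorded only in a patient who is alive, free of recurrence and still in the record at first dose. The plan does not write this as a rule; it follows from the word adjuvant and from where follow-up ends. The subgroup curve therefore cannot fall before the earliest first dose, and it falls too slowly until the last one. Patients who relapse or die early stay in the all-high-risk curve. Right-censoring does not address this.

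Two intervals from one origin would be reported without a statement that one is conditional on reaching treatment event-free. Readers of the planned abstract, poster and manuscript could take a gap between them as information about the drug. The same feature enters the Cox models, where a hazard ratio for treatment is an explicit, if exploratory, contrast.

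**Working it through.** **The plan's own figure.** Section 9.5 expects 15%-20% of about 650 patients to be high risk: 650 × 0.15 = 97.5, rounded to 98, and 650 × 0.20 = 130. This reproduces. The documents give no figure for the subgroup's size, the delay to first dose or the hazard, so what follows is illustration.

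**Assumptions.** No drug effect; no selection on prognosis; first dose s = 1, 2 or 3 months after surgery; constant hazard; 40% recurrence by T years plus 2% deaths a year. Section 7 gives up to 40% relapse, with no horizon and for regional disease, so T is varied over 3, 5 and 10 years.

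**Formulas.** h = −ln(0.6)/T + 0.02 per year. For all high-risk patients, S(t) = exp(−h·t/12), with t in months. For the subgroup timed from nephrectomy, S(t)/S(s) = exp(−h·(t−s)/12) for t > s.

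| T (years) | h per year | All, 12 months | Subgroup, s = 1, 2, 3 | Excess (points) |
|---|---|---|---|---|
| 3 | 0.1903 | 0.827 | 0.840, 0.853, 0.867 | 1.3, 2.7, 4.0 |
| 5 | 0.1222 | 0.885 | 0.894, 0.903, 0.912 | 0.9, 1.8, 2.7 |
| 10 | 0.0711 | 0.931 | 0.937, 0.942, 0.948 | 0.6, 1.1, 1.7 |

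At T = 5, a 12-month event probability of 11.5% reads 10.6% to 8.8%, which is 8% to 24% too low in relative terms. With starts spread evenly over 1 to 3 months, the subgroup curve is 1.000, 0.997 and 0.990 at 1, 2 and 3 months, against 0.990, 0.980 and 0.970 overall.

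**Against sampling error.** If 10%-20% of the 98-130 patients receive sunitinib (assumed), n is about 10 to 26. The 95% half-width is 1.96·√(0.885 × 0.115/n): 0.198 at n = 10 and 0.123 at n = 26, or about 12 to 20 points.

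**What a first-dose clock does.** Under a constant hazard, S(12+s)/S(s) = 0.885, the same as overall. When the hazard is high early, it is not enough. Take a Weibull curve with shape 0.7, S(12) = 0.700 and a common start at 3 months, so S(3) = 0.874:
- timed from nephrectomy: 0.700/0.874 = 0.801;
- timed from first dose: S(15)/S(3) = 0.754;
- overall: 0.700.

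The 10-point gap falls to about 5.

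**What a nested landmark does.** Restrict both groups to patients event-free and under follow-up at 3 months, and the subgroup to those who started by then. Under the same no-effect, no-selection assumptions both groups then follow S(15)/S(3) over the next 12 months: 0.885 with constant hazard, 0.754 with the Weibull curve.

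**Cox models.** A simulation with no drug effect used 200,000 patients, 30% intended for treatment, starts uniform over 1-4 months, censoring uniform over 6-69 months, and 40% event risk by 60 or 24 months. The ever- against never-treated event-rate ratio from nephrectomy was 0.90 (60 months) and 0.87 (24 months). Counting time before first dose as untreated gave 1.01 and 1.00. A Cox model with fixed treatment status, fitted to 20,000 of these patients, gave hazard ratios of 0.92 and 0.84. Duration entered as a fixed covariate among the treated (assumed to run to 12 months unless cut short) gave 0.19 and 0.21 per month, because an early event shortens the recorded duration.

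**The case against.** The disease-free interval after nephrectomy among patients who received adjuvant sunitinib is a legitimate descriptive quantity, and Kaplan-Meier from nephrectomy describes those patients correctly. It misleads only when read against another group or as a treatment effect, and Section 9.5 disclaims formal hypothesis testing. This stands, and it is why the nephrectomy-timed estimate should be kept and labelled. It does not answer the title-page commitment to report both results, or the Cox hazard ratios for treatment.

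Section 9.7 is also silent on the subgroup, so the plan is under-specified rather than committed to a faulty method. That is fair, but the objective's wording and the day-count storage in Section 10 both point to the nephrectomy origin.

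The size is small and rests on assumed inputs, and the 40% comes from a background statement about regional disease rather than this study's algorithm-defined high-risk group. Both points stand. However, a confidence interval does not display this error, and a larger sample would not remove it.

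A reader might infer that recent uptake makes the problem worse. Section 9.1.3 says: "Results from the part 2 study indicated that referral and treatment patterns show an increasing trend from 2018 into 2019". Section 9.2 says: "No minimum follow-up time will be required". The documents do not support that inference. The trend is not stated for sunitinib, and the excess at a fixed time depends on s and the hazard, not on how much follow-up is censored.

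**Conclusion.** The point holds as a modest one that is cheap to repair. The subgroup's nephrectomy-timed interval contains time that is event-free by selection, the all-high-risk result does not, and the plan has no correction or label. The excess is about 0.6 to 4.0 points at 12 months under delays of 1-3 months, constant hazard, no drug effect and 40% recurrence by 3-10 years plus 2% deaths a year. This is smaller than sampling error for any plausible subgroup size. The exploratory Cox models share the problem.

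Three stronger readings are not supported. A reader might infer that sunitinib patients will look better overall than they should; this component favours them, but worse-prognosis patients may be the ones treated, so the net direction is unknown. A reader might infer that the nephrectomy clock should be replaced by a first-dose clock; that would change the stated objective and, in the Weibull illustration, removes only about half the gap. A reader might infer that the part 2 report already carries this estimate; the documents do not show whether it does.

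**What to change.** **Section 9.7, subgroup.** Keep the nephrectomy-timed estimate, to match the objective, and label it as conditional on reaching treatment event-free. Add the estimate timed from first dose and the distribution of days from nephrectomy to first dose. Confirm that this derived variable is in the transferred file: Section 9.3.5 collects the therapy dates, and the Section 10 rule for endpoint dates probably covers them but does not name them. If the two groups are shown together, add the nested landmark display. Fix the landmark time before the part 3 analysis and note that part 2 results were already known. Delayed entry at first dose on the nephrectomy clock is not a substitute: if starts are similar it returns the same S(t)/S(s).

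**Section 9.7, Cox models.** Enter systemic treatment as a time-dependent covariate, with duration counted only up to the current time, or start the model at a landmark.

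**Section 9.9.** State that the subgroup and all-high-risk results are not comparable, and that the first-dose clock alone does not make them so.

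**Cost.** A few sentences, one variable check and a little more analysis, with no new abstraction. The added subgroup figure will be slightly less favourable. A landmark loses some patients: at 3 months, 1 − S(3) = 3.0% at T = 5, or about 3-4 of 98-130 patients (about 2-6 across the three horizons), plus later starters from the subgroup. It can also lose the most recent patients: a nephrectomy on 31 December 2019 has only 3.0 months of potential follow-up on 1 April 2020, the first day of the quarter planned for expanded data collection.
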